5.2.1. Primary endpoints

The following endpoints will be assessed during Part C at Weeks 26, 52, 78, 104, 130, 156, 182, and End of Study:

- Change from baseline to each assessment in a composite outcome that is the sum of the ambulation, cognition, fine motor, and swallowing components of the NPC-SS
- The change from baseline to each assessment in total NPC-SS with the hearing domain and ABR modifiers removed in the VTS-270/VTS-270 group vs. the sham control/VTS-270 group.
- Proportion of responders (defined as no change or improvement on NPC-SS total score with hearing domain and ABR modifiers removed) at each assessment
- The Blinded Clinician-CGIC at each assessment compared to baseline
- Summary of adverse events, concomitant medications, physical examinations, audiologic examination, and clinical laboratories in the VTS-270/VTS-270 group vs. the sham control/VTS-270 group.

August 27, 2018

Page 20

• Change from baseline in the EQ-5D-3L questionnaire at each assessment in the VTS-270/VTS-270 group vs. the sham control/VTS-270 group.

Change from baseline to each assessment in each of the 9 clinical domains of the NPC-

SS in the VTS-270/VTS-270 group vs. the sham control/VTS-270 group.

 Change from baseline to each assessment in the total NPC-SS with hearing domain and ABR modifier included in the VTS-270/VTS-270 group vs. the sham control/VTS-270

group.

Time to one point increase (worsening) in NPC-SS composite score in the VTS-270/VTS-

270 group vs. the sham control/VTS-270 group.

• The composite NPC-SS mean annualized rate of change (slope) from baseline to each

assessment in the VTS-270/VTS-270 group vs. the sham control/VTS-270 group.

Proportion of responders (defined as no change or improvement on NPC-SS composite

domains) at each assessment

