6.4. Safety population

The safety population will consist of all randomized subjects who receive at least one dose of

VTS-270 or sham control. The safety population will be analyzed by the actual treatment

group.

6.5.Part C open-label population

The Part C open-label population will consists of all subjects who receive at least one dose of

VTS-270 during Part C.

6.6.Device safety and tolerability substudy population

The device safety and tolerability substudy population will consist of all subjects who receive

at least one dose of VTS-270 via the IT access device in Part C.

August 27, 2018

Page 22

7. Blinded data review meeting

A blinded data review meeting will be held prior to locking the database and breaking the

blind. The purpose is to assign subjects to populations based on the above definitions.

Allocation of subjects to populations and all decisions made during this meeting will be

documented in the meeting minutes.

The following listings will be provided for the meeting and will follow definitions of the ITT,

mITT and safety populations:

• eligibility of all subjects

demographic and other baseline data

medical history

prior and concomitant medications

post-treatment efficacy assessments completed or not

To define the PP population, a listing of protocol deviations will be provided.

Missing data, visit windows, and subject withdrawals may be reviewed. Further ad hoc

listings may be provided as required.

No further definition of populations will be made after the blind data review meeting.

8. General conventions and statistical considerations

Descriptive and inferential statistics will be used to summarize results. Standard descriptive

statistics, such as tabulations by clinically relevant discretizations, the mean, median, standard

deviation, quartiles, minimum, and maximum, will be calculated for continuous variables. For

discrete variables, descriptive analyses will be based on numbers of subjects and related

percentages.

In order to control for interpretability issues that could arise from pooling Part A subjects

(randomized 3:1 treatment: sham) with the Part B subjects (randomized 2:1 treatment: sham),

and to keep the integrity of the randomization, all table presentations will display results in

two ways. First, the results will be presented by overall treatment group (one column per treatment group), similar to that shown below:

Overall	Overall		
Sham	Treatment	Total	
(N=X)	(N=X)	(N=XX)	

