n (%)	n (%)	n (%)	P-VALUE

Second, the results will be presented by treatment group, stratified by Part A vs. Part B. The layout will be presented similar to that shown below:

Part A	Part A	Part B	Part B
Sham	Treatment	Sham	Treatment
(N=X)	(N=X)	(N=XX)	(N=XX)
n (%)	n (%)	n (%)	n (%)

Additionally, all formal statistical analyses will be stratified by whether subjects were randomized into Part A vs. randomized into Part B.

For Part C, all table presentations will display results by path of entry (e.g., Part A/B Sham, Part A/B Treatment, Part C) and overall.

In addition to tabular summaries, all relevant electronic case report form (eCRF) data and external lab data will be provided in by-subject listings. All data listings, summaries, figures, and statistical analyses will be generated using SAS Version 9.4 or higher [3].

8.1.Study days

For the purpose of the analysis, the reference time (time zero) is defined as the start date/time of study drug administration for all purposes, except for the age and concomitant medication where time zero is the time when Informed Consent was granted. Randomization may occur on or before Study Visit 1 (Day 0). Protocol-defined Day 0 is the calendar date of the first administration of the study drug. Study day will be calculated relative to first administration of the study drug. Specifically:

Study day = date of visit/test/procedure – first dose date + 1.

Statistical analyses will be performed using study day as defined above. Protocol study day =

Study day if study day < 0; or (Study day - 1) if Study day ≥ 0 . All data listings will be based

on the Study day as defined above.

8.2.Baseline

The baseline value for all NPC-SS related endpoints will be based on the assessment

performed at screening. The baseline value for all other study assessments including but not

limited to vital signs, clinical outcome and disease progression measures, and concomitant

medications is defined as the last non-missing value prior to the first dose, unless otherwise

specified.

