- Individual level outcomes applied to each of the NPC-SS composite domains following 52 weeks of treatment for VTS-270 treated subjects compared to sham controls. Each individual level outcome will be assigned the value of +1 if the change from baseline is negative (i.e., the subject improves over time), 0 if the change from baseline is 0, and -1 if the change from baseline is positive (i.e., the subject declines over time). The analysis of the individual-level outcome will be based on the exact likelihood ratio test to test the null hypothesis that the values are the same across the two groups. The analysis will be applied to each of four composite domains of the NPC-SS scores separately.
- The proportion of subjects that are responders (defined as a score of 0 or +1) on each
 domain (ambulation, cognition, fine motor, swallowing) of the NPC-SS composite will
 be analyzed using the CMH test, stratified by study part.

 Cross-tabulation analysis of Clinician CGIC responders (defined as a score of no change, minimally improved, moderately improved, or markedly improved) and individual NPC-SS composite domain responders (defined as no change or improvement) at Week 52.

11.7.Subgroup analyses

Subgroup analyses will be performed on the following efficacy endpoints:

- Change from baseline in NPC-SS composite score at Week 52
- Blinded Clinician CGIC at Week 52
- Change from baseline in NPC-SS total score at Week 52
- Change from baseline in NPC-SS total score minus hearing and ABR at Week 52
- Change from baseline in individual scores for the 9 domains of the NPC-SS score at Week 52
- Composite NPC-SS mean annualized rate of change (slope) from baseline at Week 52

The endpoints above will be summarized by treatment group for the subgroups defined on the basis of the categorized variables listed below:

Grouping variable	Subgroups
Baseline Miglustat use	Yes,
	No
Baseline NPC severity	<20,
	≥20
Duration of neurological	<4,
symptoms at baseline (years)	4-8,
	>8
Post-baseline Miglustat use	Yes,
	No
Clinician-CGIC severity	Minimally worse,
	Moderately worse,

	Markedly worse

12. Safety summaries

All of the assessments in the sections below will be performed both for Part B using the Safety population and Part C using the Part C Open-Label population.

12.1.Adverse events

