worsened severity post-randomization. In case of partially missing AE start and stop dates,

the dates will be imputed by comparing to first dose date of study medication so that the

corresponding AEs will be made treatment-emergent whenever possible, unless the available

partial date information clearly indicates that the event happened outside of the treatment

CONFIDENTIAL

period. In general, a conservative strategy will be followed with respect to the assignment of AEs with partial start dates.

Presentations for Part A/B will include all adverse events with an onset date through the first Part C dose date - 1. Presentations for Part C will include all adverse events with an onset date on or after the first VTS-270 dose date. The incidence of TEAEs will be shown in terms of the total number of subjects and not in terms of the total number of events.

The following presentations of treatment-emergent adverse events will be summarized by study part and treatment group:

- Serious adverse events
- All adverse events
- Adverse events by greatest toxicity grade (greatest severity will be used where toxicity grade is missing)
- Adverse events ≥ Grade 3 toxicity (severity will be used where toxicity grade is missing)
- Adverse events related to study drug (i.e., AEs classified as possibly, probably, and definitely related)
- Adverse events related to LP procedure (Adverse events were categorized as 'related to LP procedure' if the event was marked as related to intrathecal procedure or other protocol required procedures.)
- Adverse events of special interest: Related to or resulting in hearing impairment, and seizures, other agitation, aphasia, dystonia and other neurologic AE's.
- Adverse events leading to study discontinuation.

All of the above summaries, other than the AEs related to study drug summary, will be repeated based on related AEs. All AEs will be listed with MedDRA coding, onset and resolution dates, seriousness, severity, relationship, actions, and outcome.

In addition, the adverse events for subjects who took study medication from batch will be summarized to evaluate any impact of the decrease in pH over time.

August 27, 2018

Page 42

The following subgroup analyses will also be performed.

• Treatment emergent adverse events by SOC, PT, and post-baseline Miglustat use (yes,

no)

Treatment related treatment emergent adverse events by SOC, PT, and post-baseline

Miglustat use (yes, no)

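### The Part C adverse-event window opens at the first VTS-270 dose, not the first Part C dose, so active-arm subjects carry their blinded-phase events into the Part C tables

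*SAP*

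**What the plan says.** SAP section 12.1.2 (AE summaries) defines the two reporting windows in adjacent sentences.

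- Part A/B: "Presentations for Part A/B will include all adverse events with an onset date through the first Part C dose date - 1".
- Part C: "Presentations for Part C will include all adverse events with an onset date on or after the first VTS-270 dose date".

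Incidence is per subject: "The incidence of TEAEs will be shown in terms of the total number of subjects". The opening of section 12 says the assessments are "performed both for Part B using the Safety population and Part C using the Part C Open-Label population". Section 6.5 defines that population by subject: "The Part C open-label population will consists of all subjects who receive at least one dose of" VTS-270 in Part C. Section 8 sets the columns: "For Part C, all table presentations will display results by path of entry (e.g., Part A/B Sham, Part A/B Treatment, Part C) and overall". Section 5.2.1 lists the adverse-event summary among the Part C primary endpoints and frames it, with "audiologic examination, and clinical laboratories in the VTS-270/VTS-270 group vs. the sham control/VTS-270 group", as a contrast between the two randomised paths.

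**The concern.** The Part A/B window ends at an event tied to Part C. The Part C window starts at an event that, for most rolled-over subjects, happened in the blinded phase. The two windows therefore overlap for subjects randomised to VTS-270 and not for those randomised to sham.

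Long-term safety is part of the Part C primary objective (SAP 2.3.1). An overlap on one path only would raise incidence in the VTS-270/VTS-270 column and leave the sham/VTS-270 column alone. The contrast in section 5.2.1 would then look worse for longer-treated subjects for a reason that is purely definitional. The affected tables include the hearing and neurologic events of special interest, and section 12.6 treats ototoxicity as a known risk. Part C data up to the 30 March 2018 cut-off are in the planned lock, and further Part C analyses may go into registration dossiers (section 1.2).

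**Working it through.** The plan gives no figure that depends on this window, so there is nothing to reproduce. The check compares the two windows by path of entry and then illustrates the effect.

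**Does anything else in the SAP limit the event dates?**
- The Part C open-label population (6.5) selects subjects, not events.
- The treatment-emergent definition (12.1.2) is anchored on randomisation, so it admits every Part A/B event.
- Sections 8.8 and 12.1.2 call for summaries by study part but do not restate the window.
- The SAP does write within-part dates elsewhere. The Part A/B sentence ends "with an onset date through the first Part C dose date - 1", and section 10.2 counts duration from the first dose in the study part.

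**Overlap on the nominal calendar.** Inputs: first blinded dose on Day 0 (Exhibit 2); first Part C dose taken as Week 52, Day 364 (Exhibit 3).

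| Path of entry | Part A/B window | Part C window opens | Overlap |
|---|---|---|---|
| VTS-270 to VTS-270 | to Day 363 | Day 0 | Days 0 to 363 = 364 days |
| Sham to VTS-270 | to Day 363 | Day 364 | 0 days |

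Subjects who enter Part C early, through rescue or repeated dose reduction, have a shorter overlap.

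**How many subjects.** Section 8.5 plans 35 on VTS-270 and 16 on sham. Exhibit 1 gives Part C as 51 plus up to 14 from the NIH study, 65 at most.
- 35/51 = 69% of planned randomised subjects.
- 35/65 = 54% of the Part C maximum.
- 35 × 364/365.25 = 34.9 subject-years of overlap, if all roll over at Week 52.

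**Illustration; all incidences are assumptions.** Let p be the Part A/B incidence of an event in active-arm subjects and q the true Part C incidence on every path, with the two phases independent.
- VTS-270/VTS-270 column = 1 − (1 − p)(1 − q)
- Overall column = [35 × (1 − (1 − p)(1 − q)) + 30 × q]/65, where 30 = 16 + 14

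With q = 10%:

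| p | VTS-270/VTS-270 column | Overall column | True Part C |
|---|---|---|---|
| 20% | 1 − 0.8 × 0.9 = 28% | (9.8 + 3)/65 = 20% | 10% |
| 50% | 1 − 0.5 × 0.9 = 55% | (19.25 + 3)/65 = 34% | 10% |
| 80% | 1 − 0.2 × 0.9 = 82% | (28.7 + 3)/65 = 49% | 10% |

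If the annual risk r is instead equal in both phases, with one year in Part C, the VTS-270/VTS-270 column shows 1 − (1 − r)²: 19%, 36% and 64% for r = 10%, 20% and 40%. The sham/VTS-270 column shows 10%, 20% and 40%.

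**With the Part C window opening at the first Part C dose**, the overlap is 0 days on every path.

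**The case against.** The strongest reply is that the context shows what was meant. Safety summaries are by study part, the Part C population is defined by dosing in Part C, and exposure is computed within each part. A sensible programmer would read the phrase as the first VTS-270 dose in Part C. That may well be the intent, but no sentence says it, and the neighbouring sentence names the Part C dose explicitly. Whether events are in fact shown twice depends on the programming.

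A second reply is that the wording is deliberate: a cumulative table from the start of active treatment is a recognised way to present long-term safety. The SAP states no such purpose. Such a table would also not match the Part C duration and exposure in section 10.2, which start at the first dose in that part. This reading does mean the sponsor should state its intent before the phrase is changed.

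Other limits stand. The document figures used are planned ones: 54 subjects were randomised, their split by arm is not given, and 65 is a ceiling. Part C follow-up is staggered, so the ratio of exposures between columns is unknown. The Part A/B tables, which carry the randomised safety comparison, keep a correct window. No hypothesis test on Part C adverse events is specified. Incidence is per subject, so nothing is doubled within a table, and listings with onset dates would let a reader trace the carry-over.

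**Conclusion.** The concern holds on the text as written. The Part C rule uses the wrong anchor for subjects randomised to VTS-270, and no other part of the SAP supplied corrects it. The overlap is 364 days for an active-arm subject entering at Week 52 and zero for a former sham subject. It could touch up to 35 of 65 Part C subjects, assuming planned numbers and full roll-over. The percentages above rest on assumed incidences and independence between phases. They show direction and plausible scale, not an expected result.

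The damage is confined to Part C safety reporting: the VTS-270/VTS-270 column, the overall column and the contrast with sham/VTS-270. The co-primary analyses and the type I error rate are untouched. The wording is also unclear for entrants from the NIH study, whose first VTS-270 dose precedes this trial. This should be corrected before the Part C tables are run.

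**What to change.** In section 12.1.2, define Part C events as those with onset on or after the first Part C dose date. The onset windows then do not overlap on any path of entry.

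State in the same place how an event that began earlier and worsened in Part C is handled. The natural rule is to count it in Part C if the worsening falls on or after the first Part C dose. This needs its own line, because the present treatment-emergent definition refers to randomisation.

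If a cumulative on-drug table is wanted, define it as a separate, labelled table starting at the first VTS-270 dose, with exposure counted from the same date, and say how prior dosing in the NIH study is treated.

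The cost is a sentence or two in the SAP and the matching date conditions in the programs. No additional data are needed.

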Study Design	
This is a multicenter, multinational, prospective, randomized, double-blind, sham-controlled, 3-part, efficacy and safety trial of VTS-270 administered by the lumbar intrathecal (IT) route every 2 weeks, with a planned enrollment of approximately 51 subjects (in Parts A and B) with Niemann-Pick type C1 (NPC1) disease. The study will be conducted in 3 parts: Parts A, B, and C.
 
Part A evaluated 3 different dose levels of VTS-270 versus sham control, administered as 4 lumbar IT injections every 2 weeks, to determine the dose level for Parts B and C. A total of 12 subjects were enrolled and have completed Part A.
 
Part B will evaluate the safety and efficacy of the dose selected from Part A, 900 mg, compared with sham control in approximately 51 subjects, including the 12 subjects from Part A. Subjects will receive treatment with VTS-270 for up to 52 weeks (inclusive of Part A). Subjects who elect not to continue with Part C will have 26 weeks of follow-up.
 
Part C will be an open-label extension phase of the study. Subjects who complete Part B, meet the criteria for dose reduction for a second time, or meet the rescue therapy criteria after 6 months of participation in Part B are eligible to participate in Part C. Subjects who are currently active in the National Institutes of Health (NIH) phase 1 study (Protocol 13-CH-0001) will also be eligible to participate upon completion of their participation in the phase 1 study. Additionally, subjects who have received prior written authorization from Vtesse to enroll directly into Part C are eligible to participate. Part A and B subjects who transition into Part C will receive treatment with VTS-270 until the investigator considers VTS-270 to no longer be beneficial, VTS-270 receives marketing authorization, or the development program is discontinued. NIH phase 1/2a subjects who transition into Part C will receive treatment with VTS-270 until the investigator considers VTS-270 to no longer be beneficial to the subject, VTS-270 receives marketing authorization, or the development program is discontinued.
 
A European site-specific substudy will be conducted as part of the Part C study. This substudy will assess the safety and tolerability of the B. Braun Celsite® Spinal Access Port System (hereafter generally referred to as the “device”) for the administration of VTS-270 every 2 weeks. The device is CE marked in Europe and consists of a subdermal access port connected to a catheter that is positioned in the lumbar IT space. Given that VTS-270 does not penetrate the blood-brain barrier and requires IT administration, the ability to administer VTS-270 via the device will obviate the need for biweekly lumbar punctures (LPs), as well as anesthesia, thereby removing a significant burden for subjects and site personnel. In this device safety and tolerability substudy, approximately 6 eligible Part C subjects who have received at least 3 lumbar IT doses (900 mg VTS-270) in Part C will undergo baseline assessments approximately 3 days prior to implantation of the device (same day as their last administration of VTS-270 via LP). The device will be implanted in the hospital, and the subject will remain in the hospital for 2 additional days post implantation. During the 3-day confinement period (Day 1 surgery, Days 2 and 3), subjects will be given intravenous (IV) antibiotics, which are part of the routine implantation procedure.
 
Subjects entering the European site-specific device safety and tolerability substudy will continue on their Part C schedule of assessments but will have additional device safety

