Test and Control Product, Dose, and Route of Administration	
VTS-270 will be provided in appropriately labeled vials, formulated as a 200 mg/mL injectable solution. An unblinded pharmacist/designee at each investigational site will be responsible for dispensing or preparing the assigned dosage of 900 mg for administration in 4.5 mL. In the case of dose reduction, the 600 mg dose is administered in 3 mL and the 400 mg dose is administered in 2 mL.
 
VTS-270 Administration via Lumbar Puncture and Sham Lumbar Puncture
 
In Part A, VTS-270 administration via LP and sham will be performed every 2 weeks for 4 administrations. In Part B, VTS-270 administration via LP and sham will be performed every 2 weeks for 52 weeks. In Part C, VTS-270 will be administered via LP or the device every 2 weeks. Instructions for administration via the device are presented in the following subsection.
 
The LP and/or sham is to be performed under monitored anesthesia care (conscious sedation) with an appropriate oral or IV agent and performed by an unblinded study physician. General anesthesia will be allowed on a case-by-case basis, following discussion with the medical monitor, in those subjects for whom a medical condition necessitates it.
 
Parents/caregivers will not be present in the room during lumbar IT or sham treatment. Thus, the subject and the parent will be blinded to treatment, the former a consequence of anesthesia.
 
The sham procedure will consist of 1 to 2 small needle pricks on the lower back at the location where the LP and IT injection is normally made. The needle(s) will break the skin but no lumbar puncture or needle insertion will occur. The needle prick(s) will be covered with the same bandage that is used to cover the IT injection normally, thus simulating the appearance of an IT LP injection. To maintain the blind, a similar type of anesthesia, sedation, or minimal sedation (e.g., a low dose of an anxiolytic) should be used for the sham procedure as for the subject receiving study drug, following institutional procedures. The subject will be kept in the procedure room for approximately 30 minutes, simulating the same amount of time that subjects administered study drug are kept for administration procedure.
 
VTS-270 will be administered as an IT slow bolus (1 to 2 minutes, depending on the volume administered) LP injection (maximum rate of administration = 4.5 mL/minute). The volume of the injection is determined by the dose group. Prior to the VTS-270 injection, a volume of CSF fluid approximately equal to the VTS-270 dose is to be removed. Anesthesia or sedation will be used for the IT dosing procedure, following institutional guidelines and procedures.
 
All subjects, sham and study drug, are required to lie flat with feet elevated for 30 to 45 minutes following dosing. For the 3 days following each procedure, subjects in both the sham and active treatment groups are to avoid acoustic overstimulation and minimize exposure to loud noises, e.g., headphones for music or video games.
 
Device Administration (European Site-Specific Device Safety and Tolerability Substudy, Part C)

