12.8. Neurological evaluation

Neurological evaluations will be summarized at baseline and at subsequent follow-up weeks

by study part and treatment group.

12.9.12-lead ECG

Summaries will present the results of 12-lead ECG testing.

12.10.Serum pregnancy

Serum pregnancy test results will be listed.

12.11.Device safety and tolerability substudy

The following safety evaluations will be listed and/or summarized for the B. Braun Celsite

Spinal Access Port utilized to administer VTS-270 in the device safety and tolerability

substudy of subjects in Part C. Descriptive statistics used will be appropriate to the type of

measurement (continuous or discrete).

Wound check, examination of port site and catheter track at access port infusion visits

CONFIDENTIAL

August 27, 2018 Page 46

Intracranial pressure (ICP) via LP

Device implant procedure data will be listed.

13. Appendices

13.1.NPC Clinical Severity Scale

Table A1. NPC Clinical Severity Scale			
Ambulation	Score	Eye Movement	Score
Normal	0	Normal eye movement	0
Clumsy	1	Mild vertical supranuclear gaze palsy (VSGP), detected by physician only	1
Ataxic unassisted gait or not walking by 18 months	2	Functional VSGP, noted by family or compensation with head movements	2
Assisted ambulation or not walking by 24 months	4	Total VSGP, abnormal horizontal saccades may be present	3
Wheelchair dependent	5	Total ophthalmoplegia (vertical and horizontal saccades absent)	5
Speech	Score	Swallow	Score
Normal speech	0	Normal, no Dysphagia	0
Mild dysarthria (easily understood)	1	Cough while eating*	
		Intermittent Dysphagia w/liquids	+1
		Intermittent Dysphagia w/solids	+1
Severe dysarthria (difficult to understand)	2	Dysphagia w/liquids	+2
		Dysphagia w/solids	+2
Non-verbal/functional communication skills for needs	3	Nasogastric tube or gastric tube for supplemental feeding	4
Minimal communication	5	Nasogastric tube or gastric tube feeding only	5
Fine Motor Skills	Score	Cognition	Score
Normal	0	Normal	0
Slight dysmetria/dystonia (independent manipulation)	1	Mild learning delay, grade appropriate for age	1
Mild dysmetria/dystonia (requires little to no assistance, able to feed self without difficulty)	2	Moderate learning delay, individualized curriculum or modified work setting	3
Moderate dysmetria/dystonia (limited fine motor skills, difficulty feeding self)	4	Severe delay/plateau, no longer in school or no longer able to work, some loss of cognitive function	4

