Neurological examination ^f	X													X	
Clinical laboratory testing ^g	X							X						X	
12-lead ECG	X														
Audiologic testing	X	X	X#	X#	X#	X				X				X	
Auditory brainstem response	X					X#									

August 27, 2018 Page 50

Visit Number		1	2	3	4	5	6	7	8	9	10	11	12	13	14
Study Day	Day -45 to Day -1	0	14	28	42	56	70	84	98	112	126	140	154	168	182
Window (days)			(±3)	(±3)	(±3)	(±3)	(±3)	(±7)	(±7)	(±7)	(±7)	(±7)	(±7)	(±7)	(±7)
Time Point (Week)	Screening	1 st Study Dose	2	4	6	8	10	12	14	16	18	20	22	24	26
NPC Clinical Severity Intake	X	X				X				X				X	
Clinician-CGIC ^h and Caregiver-CGIC		X				X				X				X	
TUG Test		X				X				X				X	
9-Hole Peg Test		X				X				X				X	
EQ-5D-3L QoL		X				X				X				X	
Confirm subject eligibility		X													
Randomizationi		X													
Collect plasma biomarker samples ^j		X				X#		X						X	
Sham or lumbar puncture and study drug administration		X	X	X	X	X	X	X	X	X	X	X	X	X	X
Collect CSF samples (study drug subjects only)		X				X#		X						X	
Collect whole blood for genetic testing		X													
Adverse events ^k		X	X	X	X	X	X	X	X	X	X	X	X	X	X
Concomitant medications		X	X	X	X	X	X	X	X	X	X	X	X	X	X

CGIC = Clinical Global Impression of Change; CSF=cerebrospinal fluid; ECG = electrocardiogram; hx=history; NPC = Niemann-Pick disease, type C; NPC1=Niemann-Pick disease, type C1; QoL=quality of life; TUG=timed up and go

 $^{^{\}rm a}$ Medical history includes history of NPC1 disease, diagnosis date, and prior treatments.

^b Urine will be obtained for urinalysis and biomarker testing

August 27, 2018

Page 51

^c Full physical exam at Screening; abbreviated physical exam at all other visits.

 $^{^{}m d}$ Vital signs, including blood pressure, will be recorded following a 5-minute rest in supine position.

^e A second set of vital signs will be recorded following recovery of sedation from lumbar puncture or sham procedure.

 $^{^{}m f}$ Full, videotaped neurological exam at Screening and Week 52; brief, videotaped neurological exam at Week 24.

^g Clinical laboratory tests include chemistry, hematology, and coagulation.

^hBlinded Clinician to meet with subject and assess overall status and functionality that will form baseline for future Clinician-CGIC assessments.

ⁱ Randomization may occur on or before Study Visit 1, Day 0, after receipt of NPC Clinical Severity Score from central rater to confirm eligibility.

^j Plasma samples for biomarkers should be obtained prior to intrathecal or sham treatment.

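### The AE summary labelled as LP-related also pools events from other protocol-required procedures, and no planned table separates port-related from LP-related events (minor, descriptive safety only)

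*SAP*

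**What the plan says.** SAP 12.1.2 (AE summaries) lists the planned presentations and introduces them with: "The following presentations of treatment-emergent adverse events will be summarized by study part and treatment group". The unit of counting is the subject: "The incidence of TEAEs will be shown in terms of the total number of subjects". One presentation covers events related to the LP procedure, with this rule: "Adverse events were categorized as 'related to LP procedure' if the event was marked as related to intrathecal procedure or other protocol required procedures". The same section repeats this summary for related events. SAP 12 states that the safety assessments are run for Part B and again for Part C.

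SAP 8.8 describes the intended content more narrowly, as events related to study treatment and to the administration procedure.

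Other text that bears on the rule:
- Sham procedure (Protocol synopsis, Test and Control Product): "The needle(s) will break the skin but no lumbar puncture or needle insertion will occur".
- Sedation in both arms (same section): "The LP and/or sham is to be performed under monitored anesthesia care (conscious sedation) with an appropriate oral or IV agent".
- Blood sampling (SAP 13.2, notes to the Parts A and B schedule): "Clinical laboratory tests include chemistry, hematology, and coagulation". The exploratory objectives in both documents also have plasma collected from sham subjects.
- Port surgery in the Part C device substudy (Protocol synopsis, Study Design): "The device will be implanted in the hospital, and the subject will remain in the hospital for 2 additional days post implantation".
- Device reporting (SAP 12.11): wound, port-site and catheter-track checks and intracranial pressure are listed and/or summarized. For the surgery itself: "Device implant procedure data will be listed".

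**The concern.** The rule joins two attributions with an *or* and names the result after one of them. Nothing limits the second attribution to the lumbar puncture. A reader of the table would take it as the incidence of LP harm, when it is the incidence of harm from any required procedure.

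Two comparisons could be blurred. In Parts A and B, events that arise equally in both arms from other procedures raise both columns and narrow the contrast between repeated LP and sham. In Part C, an implantation event marked as due to a required procedure would carry the LP label. Yet the protocol presents the port as a way to avoid repeated LPs, and its safety is a secondary objective of Part C. The harms of the port and of the LP it replaces should therefore be distinguishable.

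**Working it through.** **Step 1: does the text do what the concern says?** There is no figure in the plan to reproduce, so the passages are compared.

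| Element | Source | Bearing |
|---|---|---|
| Row definition | SAP 12.1.2 | Intrathecal procedure or any other required procedure |
| Stated intention | SAP 8.8 | Administration procedure only; narrower |
| Causality scale | SAP 12.1 | Given for study drug; none described for procedures |
| Required procedures besides LP/sham and its sedation | SAP 13.2; Protocol synopsis | Blood sampling in both arms; port implantation in the Part C substudy |
| Part C column layout | SAP 8 | By path of entry, not by port versus LP |
| Substudy endpoints and reporting | SAP 5.2.2, 12.11 | Local checks, intracranial pressure, implant data; no device-related AE table |

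The definition is wider than both its own label and SAP 8.8. No other section supplies incidence by type of procedure. Port infusions are themselves intrathecal, so their events could enter through either half of the rule. Splitting the two halves would therefore not isolate the port; that needs its own row.

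**Step 2: size of the effect on the active-sham contrast.** Let p be the true incidence of LP/sham-related events in an arm. Let q be the incidence of other-procedure events, taken as equal in both arms and independent of the first kind. Because subjects are counted once:

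- Tabulated incidence = 1 - (1 - p)(1 - q).
- Tabulated difference = (p_active - p_sham)(1 - q).

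The documents give no rates. All values of p and q below are assumptions.

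With p = 40% active and 5% sham (true difference 35 points, true ratio 8.0):

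| q | Active | Sham | Difference | Ratio |
|---|---|---|---|---|
| 5% | 1 - 0.60 × 0.95 = 43.0% | 1 - 0.95 × 0.95 = 9.75% | 33.25 points | 4.4 |
| 10% | 1 - 0.60 × 0.90 = 46.0% | 1 - 0.95 × 0.90 = 14.5% | 31.5 points | 3.2 |
| 30% | 1 - 0.60 × 0.70 = 58.0% | 1 - 0.95 × 0.70 = 33.5% | 24.5 points | 1.7 |

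With p = 20% active and 0% sham, q from 10% to 30% gives 28% versus 10% up to 44% versus 30%. The difference is 18 down to 14 points instead of 20. On the planned 16 sham subjects (SAP 8.5), that is 16 × 0.10 = 1.6 to 16 × 0.30 = 4.8 subjects shown with an LP-related event.

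The difference moves modestly at low q. The ratio moves much more, because the sham rate is small.

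**The case against.** Several stronger readings are tempting, and the documents do not support them.

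- *Sham subjects should not appear in an LP table.* A sham column is the comparator the table needs, and SAP 12.6 has events recorded by a blinded AE rater, who is not meant to know LP from sham. The fault lies in the pooling and the label.
- *Sedation events are contamination.* The protocol has the LP or sham performed under sedation and counts anesthesia as part of the burden that the port would remove. A sedation event can fairly be read as a harm of the administration procedure. In Parts A and B this leaves mainly blood sampling as the other procedure.
- *Port-surgery events will count as LP events.* The rule does not name them. They enter only if marked as due to a required procedure. The case report form is not in the supplied text, so a separate device or anesthesia field cannot be ruled out.
- *The two attributions already exist as separate data.* The wording suggests this but also fits a single combined field.
- *The ratio falls from 8.0 to 1.7.* That is one assumed scenario at q = 30%. At q of 5% to 10% the ratio is 4.4 to 3.2, and the active excess stays plain.

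There is also mitigation. Events are summarized by system organ class and preferred term, and each is listed with its relationship. The device part concerns about 6 open-label subjects with no concurrent sham arm, and SAP 12.11 does cover local port checks. No test or decision rule depends on this table.

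These arguments reduce the weight of the point but do not remove it. The label still misstates the rule, and neither term-level tables nor listings give incidence by procedure type.

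**Conclusion.** The point holds as a minor reporting fault. The summary in SAP 12.1.2 is named after the LP but defined as any required procedure, and it does not match SAP 8.8. No planned table distinguishes port-related from LP-related events in Part C.

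The size is unknown because the documents give no event rates. Under equal and independent other-procedure incidence q, the active-sham difference is multiplied by (1 - q). For q of 5% to 30% and an assumed true difference of 35 points, the table would show about 33 to 25 points. If q differed between the arms, that factor would not apply. The illustration concerns the sham-controlled parts only; in Part C the effect is a mixed label, not a diluted contrast. Nothing here touches the efficacy analyses, the type I error rate or power.

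**What to change.** 1. Relabel the pooled row *any procedure-related*. This costs nothing and holds whatever the case report form contains.
2. Where the two attributions are recorded separately, add two rows: (a) related to the intrathecal or sham administration procedure, stating that sedation for that procedure belongs here; (b) related to other protocol-required procedures. Row (a) then matches SAP 8.8.
3. In Part C, add a row for port- or implantation-related events in device subjects.
4. State the scale on which relatedness to a procedure is judged, since SAP 12.1 gives one for study drug only.

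The cost is a few extra descriptive tables with small counts. If the case report form holds only one combined field, items 1 and 4 remain, together with a table of adverse events restricted to device subjects in place of items 2 and 3.
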